Long-term outcomes of successful chronic total occlusion percutaneous coronary interventions using the antegrade and retrograde dissection and re-entry approach.

(LOTUS-ADR/RDR)

Protocol

Sponsored by: Department of Cardiology, Xi'jing Hospital.

The Fourth Military Medical University (FMMU)

Approved by: Ethics Committee, Xi'jing Hospital. FMMU

Approved Ethical Number: KY20172019-1

Approved date: 2017.03.15

Last Update: 2018.11.20

Study Time: 2018.12.01- 2019.12.30

Versions: V2.0

ABSTRACT

BACKGROUND: Chronic total occlusion (CTO) angioplasty is one of the most challenging procedures remaining for the interventional operator. Today, with contemporary CTO negotiation available strategies and significant operator expertise, the literature reports a 50-95% success rate for recanalizing CTOs. But PCIs of CTO lesions still carry a high rate of in-stent restenosis (ISR). Because previous reports have not specifically compare contemporary antegrade and retrograde dissection and re-entry dissection (ADR/RDR) technique on the long-term impact of ISR, so the investigators focused on the objective.

OBJECTIVES: This study hope to evaluate the frequency of angiographic ISR and further elucidate some ISR related higher risk factors among CTO PCI patients in intimal stent group using antegrade or retrograde wire escalation (AWE/RWE) techniques and sub-intimal stent group using contemporary antegrade or retrograde dissection and re-entry (ADR and/or RDR).

METHODS: A total of 300 consecutive selected patients with CTO lesion who will undergo successful revascularization by AWE/RWE and ADR/RDR techniques treatment will be enrolled in this prospective multicenter registry from December 1 2018 to December 31 2019. The primary study endpoint of the protocol is the binary in-stent restenosis of CTO vessels at angiographic follow-up about 13 months. The secondary endpoints are: 1) CTO technique and procedure success rate; and 2) in-hospital and 30 days MACE (Cardiac death, acute myocardial infarction, urgent repeat target vessel revascularization with either pericardiocentesis or surgery and stroke and stent thrombosis and stroke); 6months and 1-year and 2-year MACE including death, MI, and target CTO vessel revascularization and stroke ; and 3) Restenosis scores (R-scores) of related risk factors.

CONCLUSIONS: This study expect to identify long-term effect of ADR and RDR methods on the ISR incidence and predictors.

INTRODUCTION

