Chronic total occlusion (CTO) angioplasty is encountered in 18.4% to 52% of patients with coronary artery disease (CAD) undergoing coronary angiography¹⁻⁴. Observational studies suggest that successful CTO PCI can provide significant clinical benefit to patients, including symptom relief, improved left ventricular function, reduced risk of arrhythmias, and better tolerance of an acute coronary syndrome⁵. CTO is considered one of the most difficult lesion types to treat. With the development of new techniques and dedicated devices, procedural success rates for CTO recanalization have vary between 60% and 90% in recent years⁶⁻¹⁰.

However, CTO lesions have a 1.4- to 5-fold higher rate high risk of in-stent restenosis (ISR), compared with non-occlusive stenosis¹¹⁻¹⁶. ISR, induced by neointimal hyperplasia, is a long-recognized, chronic complication following PCI. Previous studies have reported clinical or lesion-related characteristics (i.e., complex lesion morphology or comorbidities, such as diabetes mellitus)^{17, 18} and calcification and CTO length are known as ISR predictors¹⁹. Whereas Valenti et al. reported that specific techniques (the subintimal tracking and re-entry technique (STAR) was associated with ISR¹¹.

The STAR technique was the first reported antegradesubintimal dissection and reentrymethod to re-open occluded arteries^{20,21}. Although this technique has some limitations, notably the inability to control the reentry point in the distal lumen, it did effectively demonstrate that blunt dissection through the subintimal space could rapidly and safely traverse even very long, tortuous, and calcified occluded segments without vessel perforation²⁰⁻²⁴. This demonstration provided the confidence to further explore the use of the subintimal space for therapeutic purposes²³. STAR was integrated into a retrograde approach (e.g. Controlled Antegrade and Retrograde subintimal Tracking (CART))²⁵⁻²⁷, and a dedicated antegradedissection and re-entry system (CrossBoss™ Catheter and Stingray™ System)²⁸. As a result of these advances and greater operator experience, success rates of CTO PCI have increased²⁹.

There have been concerns raised that the high restenosis rate after STAR³⁰⁻³³ may

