be a direct consequence of subintimal stenting. If the cause of the high incidence of restenosis is, in fact, due to use of the subintimal space, newer CTO techniques, which are based on controlled subintimal dissection and reentry methods, also would be expected to be associated with this adverse outcome²⁵⁻²⁸ Now there are only limited data about procedural success of ADR and RDR and retrograde techniques have been demonstrated and the use of subintimal stenting did not adversely impact outcomes^{34, 35}. While prospective studies with longer follow-up are needed to assess the long-term safety and efficacy of sub-intimal stenting.

The purpose of the study was therefore to examine the longer-term outcomes of patient who underwent successful CTO PCI in our program, compare the effect of ADR/RDR on outcomes with everolimus-eluting stents (EES) and assess predictors of long-term events.

METHODS

1. Trial overview and study population.

① This clinical trial is a prospective, exploratory, nonrandomized, multicenter trial evaluating the frequency of angiographic restenosis and clinical outcomes among patients undergoing CTO PCI in intimal stent group using antegrade or retrograde wire escalation (AWE/RWE) techniques and sub-intimal stent group using contemporary antegrade or retrograde dissection and re-entry (ADR or RDR) with everolimus-eluting stents (XIENCE Coronary Stent).

② According to high patient's volume registry studies in CTO lesions, the patients percentage of ADR or RDR strategy application was just only 20-25%³⁶⁻³⁷. If to get 60 patients for ADR or RDR strategies, the minimum CTO number are 300 patients. So in our registry study, 300 CTO cases, to which PCI will be attempted, are prospectively enrolled from December 1 2018 to December 31 2019 in the CTO registries of ten centers. The study was approved by the institutional review board at each site. For patients with multiple treated CTO, only the first CTO attempted was considered for the analysis.

③ Exclusions included age <18-years-old or >85-years-old, left ventricular ejection

fraction $\leq 30\%$, allergy to medications (antiplatelet drugs, heparin, metal alloys, or contrast agents), a planned surgery within 6 months of PCI or planned thrombolysis, pregnant, a life expectancy of <6 months.

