For the main analysis, the investigators consider that the lesion is crossed with dissection/re-entry when (1) a wire-based antegrade dissection was performed followed by re-entry into the true distal lumen with a straight or knuckled wire/CrossBoss, (2) A Stingray system was used to cross from the false lumen to the true lumen, and (3) when a reverse-controlled antegrade and retrograde re-entry technique is used to cross the CTO segment. Other CTO crossing techniques were considered “intraplaque,” “true-to-true,” or wire escalation techniques(as **figure 1**).

3. Intervention Procedures

- ① All patients receive optimal intravenous hydration the days before and after PCI.
- ② Patients receive an initial bolus of intravenous unfractionated heparin (100 IU/kg). The activated clotting time is monitored every 30 min to determine if an additional bolus of unfractionated heparin is necessary to maintain an activated clotting time >250s. Upstream use of glycoprotein IIb/IIIa inhibitor therapy or bivalirudin is avoided.
- ③ All procedures are performed via the radial or/and femoral route, with double coronary cannulation and contralateral selective injection. Seven-French guiding catheters are used in most cases.
- ④ All operators have received proctoring in AWE, antegrade dissection re-entry (ADR), retrograde wire escalation (RWE) and retrograde dissection re-entry (RDR) approaches used in the hybrid algorithm. And operators have performed a career minimum of 300 CTO cases.
- ⑤ To adjust the patients number in intimal stents group and subintimal stents group with either the antegrade or the retrograde approach, wire escalation technique was made as the first choice in all patients, if failed, to choose which CTO revascularization strategy is left to the operator’s discretion (Fig 1). The selection of the optimal initial CTO crossing strategy is dependent on the anatomy of the coronary vessels. Four angiographic characteristics are used to make the decision (Fig. 1): (a) lesion length (lesions ≥ 20 mm in length tend to have lower success rates and longer procedure times using standard antegrade wire escalation); (b) proximal cap location and morphology; (c) size, quality (i.e. vessel size and presence of luminal stenoses

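### The main-analysis rule names reverse CART as its only explicitly retrograde limb, so other retrograde dissection crossings could be counted as intimal (minor; clarify the coding)

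*Combined protocol and SAP*

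**What the plan says.** The groups are defined by technique in two places. The Abstract (Objectives) sets an "intimal stent group using antegrade or retrograde wire escalation (AWE/RWE) techniques" against a "sub-intimal stent group using contemporary antegrade or retrograde dissection and re-entry (ADR and/or RDR"). Methods section 1, item 1, repeats the contrast with a "sub-intimal stent group using contemporary antegrade or retrograde dissection and re-entry (ADR or RDR"). Neither place limits RDR to one method.

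The paragraph that closes Methods section 2, after item 9, gives the working rule for the main analysis. A lesion counts as crossed by dissection/re-entry under three numbered limbs:

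- Limb 1: "a wire-based antegrade dissection was performed followed by re-entry into the true distal lumen", by wire or CrossBoss.
- Limb 2: a Stingray crossing from false to true lumen.
- Limb 3: "3) when a reverse-controlled antegrade and retrograde re-entry technique is used to cross the CTO segment".

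The limbs are joined by *and*, without saying that any one is enough. The next sentence begins "Other CTO crossing techniques were considered" and places the remainder in the intraplaque, true-to-true or wire escalation class, with a pointer to Figure 1.

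Three other places bear on how retrograde cases fall:

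- The Introduction says "STAR was integrated into a retrograde approach (e.g. Controlled Antegrade and Retrograde subintimal Tracking (CART"), so CART is both retrograde and subintimal in the protocol's own terms.
- Methods section 2, item 8, says that retrograde knuckling is usually, but not always, followed by reverse CART. It names no other ending.
- Methods section 3, item 5, lists CART and reverse CART as separate techniques in use. Item 6 records each case's approach as AWE, ADR, RDR or RWE.

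**The concern.** The main-analysis rule decides which group each patient's restenosis result is counted in. By the group definitions the comparator is AWE/RWE. By the main-analysis rule it is whatever the three limbs leave over. The two agree only if every retrograde dissection crossing meets one of the limbs.

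CART is the visible case where they may not agree. It is listed apart from reverse CART, so limb 3 cannot safely be read to cover both. A retrograde dissection that ends in some other way is a second possibility, though no such ending is described.

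The study asks whether use of the subintimal space raises restenosis. Placing subintimal crossings in the intimal group would pull the comparison toward no difference if it does, and would take cases from the smaller group. Ten centres enrol, so the same crossing could also be coded in different ways unless the rule is explicit.

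**Working it through.** **Step 1. Follow one case through both definitions.** Take a CART crossing without Stingray.

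| Source | Test applied | Group |
|---|---|---|
| Abstract; Methods 1, item 1 | Retrograde dissection and re-entry? Yes, on the Introduction's description of CART | Sub-intimal |
| Methods 2, main-analysis rule, limb 1 | Wire-based antegrade dissection with re-entry? Not stated for CART | Open |
| Same rule, limb 2 | Stingray? No | Not met |
| Same rule, limb 3 | Reverse CART? No | Not met |
| Same rule, residual sentence | Anything else | Intimal, if limb 1 is not met |

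The conflict exists if CART fails limb 1 and Figure 1 does not say otherwise. The visible text settles neither point.

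**Step 2. Reproduce the planning figure.** Methods section 1, item 2, states that "the patients percentage of ADR or RDR strategy application was just only 20-25" (per cent) and derives 300 patients from a target of 60.

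- 60 / 0.20 = 300, the stated figure. (60 / 0.25 = 240.)
- With 300 patients: 300 × 0.20 = 60 or 300 × 0.25 = 75 sub-intimal cases, leaving 240 or 225 comparators.

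**Step 3. Effect of moving cases.** Let n0 be the true number of comparators, p1 and p0 the restenosis rates, and m the number of sub-intimal cases coded as intimal. Assume that moved cases have rate p1. Then:

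- Observed comparator rate = (n0·p0 + m·p1) / (n0 + m)
- Observed difference = (p1 − p0) · n0 / (n0 + m)
- Relative shrinkage = m / (n0 + m), whatever the rates

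The documents do not give m; 1, 3 and 6 are assumptions. The last row also assumes that 70% of 60 and 240 have follow-up (42 and 168).

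| Comparators n0 | m = 1 | m = 3 | m = 6 |
|---|---|---|---|
| 240 | 0.4% | 1.2% | 2.4% |
| 225 | 0.4% | 1.3% | 2.6% |
| 168 | 0.6% | 1.8% | 3.4% |

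For scale, a 10% shrinkage would need 27 of 60 cases to move (27/267 = 10.1%), or 25 of 75 (25/250 = 10.0%).

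**Step 4. Illustration on the risk scale.** Assume 24% versus 12%. At m = 6 the expected difference goes from 12.0 points to 12.0 × 240/246 = 11.7 points (also 11.7 with 225/231). The 95% Wald half-width is 1.96 × √[p1(1−p1)/(n1−m) + pc(1−pc)/(n0+m)], where n1 is the true number of sub-intimal cases and pc the observed comparator rate.

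| True groups | Half-width, m = 0 | Half-width, m = 6 |
|---|---|---|
| 60 / 240 | 11.6 points | 12.1 points |
| 75 / 225 | 10.6 points | 10.9 points |

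At assumed rates of 20% versus 10% and 30% versus 15%, the half-width widens by 0.4 to 0.6 points at m = 6.

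**Step 5. Group size.** The sub-intimal group becomes 60 − m to 75 − m. Starting from 75, it stays at 60 or more up to m = 15.

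**The case against.** The strongest reply is that part of the rule cannot be seen here. The residual sentence points to Figure 1, and the figure may class CART as RDR. That stands: it would be wrong to say that the plan leaves CART unclassified. But if the figure does so, a sentence that names only reverse CART still needs to be brought into line with it.

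Second, the Abstract and Methods section 1 use a general label, and a more specific working rule under a general label is not in itself a contradiction. One arises only if a crossing is RDR and also fails every limb. CART may meet limb 1: its full name includes antegrade tracking, and the Introduction traces it to STAR, an antegrade dissection and re-entry method. Limb 2 is not confined to antegrade procedures in the rule's wording either. This too stands. It is why limb 3 is called the only *explicitly* retrograde limb, and why the point is limited to cases that meet no other limb.

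Third, the number affected could be zero. CART appears in Methods only in a general list of guidewire strategies, and the retrograde pathway in Methods section 2, item 8, names only reverse CART for re-entry. Nothing in the documents contradicts this.

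A reader might infer that the rule materially biases the main comparison, costs worthwhile power, or leaves the sub-intimal group short of 60. The documents support none of these. They give no CART frequency, describe the study as exploratory and state no power target. The planned 20-25% share allows up to 75 sub-intimal cases.

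**Conclusion.** The point holds as a minor inconsistency in how exposure is classified for the main analysis. On the visible text, a CART crossing, or another retrograde dissection/re-entry not finished by reverse CART, is counted as intimal unless it also meets limb 1 or limb 2, although the stated groups place RDR on the sub-intimal side.

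The likely effect is slight: relative shrinkage of 0.4% to 3.4% over the assumed range, or about 0.3 of a point on an assumed 12-point difference whose 95% half-width is 11 to 12 points. This rests on assumed m, assumed rates, and moved cases restenosing like other sub-intimal cases. The direction is toward no difference, and only if subintimal stenting does raise restenosis. The case for acting is that the rule should assign each crossing to one group before outcomes are known, not that a large error has been shown.

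**What to change.** In the main-analysis paragraph of Methods section 2:

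1. State that the three limbs are alternatives, so that meeting any one is enough.
2. Leave limb 1 and limb 2 as worded. Extend limb 3 to any retrograde dissection with re-entry recorded as RDR, including CART as well as reverse CART.
3. State that the comparator then holds only AWE/RWE crossings, as in the Abstract and Methods section 1.
4. Check Figure 1 and make it and the text agree.

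The approach field in Methods section 3, item 6, is already recorded. The cost is therefore one reworded rule, one coding line for CART and a check of the figure, with no new data or adjudication. The change concerns analysis classification only and has no bearing on which crossing technique operators use.

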④ Clinical success will be defined as a procedural success without In-hospital MACCEs. In-hospital MACCEs is defined as the composite of non-Q-wave and Q-wave myocardial infarction (MI), recurrent angina requiring urgent repeat revascularization with PCI or coronary bypass surgery, stroke, and death. Non-Q-wave MI is defined as creatine kinase-MB enzyme elevation >3 times the upper limit of normal. When new pathological Q waves, in addition to enzyme elevation, will be observed on the electrocardiogram, the event is defined as a Q-wave MI. In all patients, creatine kinase and creatine kinase-MB is evaluated 6 h after the procedure and until their normalization if levels is abnormal.

⑤ Lesion complexity will be judged using the J-CTO (Multicenter CTO Registry in Japan) score (0 ¼ easy, 1 ¼ intermediate, 2 ¼ difficult, 3 ¼ very difficult) (20) and calculated by allocating 1 point each for: non-tapered proximal cap (ie, blunt or ambiguous), any calcification, any tortuosity, occlusion length >20 mm and any prior unsuccessful attempt. J-CTO score of ≥ 2 was defined as complex.

⑥ CTO proximal cap location is defined according to American Heart Association (AHA) classification and additionally coded as either ostial or non-ostial and proximal (left main, proximal left anterior descending, proximal circumflex or proximal right coronary artery) or distal (all other sites). Cap morphology is coded as blunt or tapered, or as ambiguous when there is lack of clarity over the origin of the ongoing vessel. Calcification within the CTO is coded as none visible, mild (spots only), moderate (<50% of vessel circumference) or severe (>50% of vessel circumference). Tortuosity is assessed at baseline or after subsequent equipment passage and coded as straight (no bend or <45° single bend), slight (>45° single bend), moderate (2 bends >45° or 1 bend >90°) or severe (2 bends >90° or 1 bend >120°).

Disease proximal and distal to the CTO is classified as absent, mild, moderate or severe. Proximal or distal cap side branch is considered present if occurring ≤ 3 mm from the respective CTO cap. Occlusion length is estimated by dual injection, or from apparent length after guidewire crossing. Collaterals are classified according to Cohen and Rentrop and deemed interventional if, on angiographic inspection, are thought amenable to crossing by a guidewire and a microcatheter by the operator.

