and/or calcification) and presence of side branches of the target coronary vessel at the distal cap; and (d) size and suitability of collateral circulation for the retrograde technique. Several guidewire strategies are used, including the single-wire technique, the parallel-wires technique, the intravascular ultrasound–guided wiring technique, and retrograde wiring through collateral vessels, such as simple retrograde wiring, kissing wires, the knuckle technique, and the CART and reverse CART techniques, as previously described.

⑥ The number and type of approaches (AWE/ADR/RDR/RWE) required to cross the CTO segment are recorded. Wire crossing time is from insertion of the guidewire into either the target vessel or retrograde donor vessel to when the wire successfully crossed the CTO segment and re-entered the true lumen.

⑦ The occluded segment is stented with second generation DESs(XIENCE, Abbott) (if no contraindication for prolonged dual antiplatelet therapy) and post-dilation performed to optimize stent expansion and apposition as needed.

⑧ In this study, by evaluating CTO lesions in the pre-stenting and post-PCI period, the investigators seek to identify the predictors of ISR. The standard restenosis scores (R-scores) related six factors including: A: the number of stent ($n < 2$ 0score; $2 > n < 4$ 1score; $n > 4$ 2score); B: stent length ($< 35\text{mm}$ 0score; $36\text{-}70\text{mm}$ 1score; $> 71\text{mm}$ 2 score); C: lumen dissection length ($< 20\text{mm}$ 0score; $21\text{-}30\text{mm}$ 1score; $> 31\text{mm}$ 2score) ; D: calcification (mild 1score; severe 2score; E: lumen area ($< 5\text{mm}^2$ 3score; $5\text{-}7\text{mm}^2$ 2score; $> 7\text{mm}^2$ 1score) and F: angulation slight ($> 45^\circ$ single bend 1score), moderate (2 bends $> 45^\circ$ or 1 bend $> 90^\circ$ 2 score) or severe (2bends $> 90^\circ$ or 1bend $> 120^\circ$ 3score). Additionally, the investigators will utilize IVUS as a tool to evaluate predictor factors to obtain in-depth analyses of the lesions.

[figure not shown]

Figure 1: CTO PCI techniques in trial

4. Statistical analysis

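### The restenosis score (secondary endpoint 3) cannot be applied as written: its bands leave the scores for two stents, four stents and moderate calcification open

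*Combined protocol and SAP*

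**What the plan says.** Methods 2 (Study endpoints and definitions), item 1 lists the R-score as the third secondary endpoint. Its scoring is set out only in Methods 3 (Intervention Procedures), item 8, which has six components, A to F:

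- **A, stent count:** "A: the number of stent ($n < 2$ 0score; $2 > n < 4$ 1score; $n > 4$ 2score".
- **B, stent length:** "B: stent length ($< 35\text{mm}$ 0score; $36\text{-}70\text{mm}$ 1score; $> 71\text{mm}$ 2 score".
- **C, dissection length:** "C: lumen dissection length ($< 20\text{mm}$ 0score; $21\text{-}30\text{mm}$ 1score; $> 31\text{mm}$ 2score".
- **D, calcification:** "D: calcification (mild 1score; severe 2score", with no further grades.
- **E, lumen area:** under 5 mm² scores 3, 5 to 7 mm² scores 2, over 7 mm² scores 1.
- **F, angulation:** slight 1, moderate 2, severe 3.

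The grades behind D and F are defined in Methods 2, item 6. For calcification: "Calcification within the CTO is coded as none visible, mild (spots only), moderate" and, continuing, "moderate (<50% of vessel circumference) or severe (>50% of vessel circumference". For tortuosity, the lowest grades are "coded as straight (no bend or <45° single bend), slight (>45° single bend".

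Methods 4 (Statistical analysis) does not mention the R-score. No section says whether the six components are added up or used one by one, or how a value outside the printed bands is to be scored.

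**The concern.** A score can be computed only if every value that can be recorded falls in exactly one band. Item 8 fails that test for common values, not only at the edges: stent counts of two to four as printed, and a whole calcification grade.

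Two things follow. First, two people scoring the same patient from the same text can reach different answers, and the registry draws on ten centres. Second, if the missing scores are settled only at analysis, they can be settled with the 13-month restenosis results in view. The component concerned would then tend to look more predictive than it is.

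**Working it through.** The plan gives no figure to reproduce here. The check is whether each band, read as a logical rule, gives each recordable value exactly one score.

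**Item A.** Inputs: the three printed bands, and one to five or more stents.

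| Reading | 1 | 2 | 3 | 4 | 5+ |
|---|---|---|---|---|---|
| As printed (n below 2 and below 4 for score 1) | 0 and 1 | none | none | none | 2 |
| First sign reversed, 2<n<4 | 0 | none | 1 | none | 2 |
| Outer bands kept strictly, so 2 to 4 = 1 | 0 | 1 | 1 | 1 | 2 |
| Signs read loosely: up to 2 = 0, 3 = 1, 4 or more = 2 | 0 | 0 | 1 | 2 | 2 |

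The last two rows are both complete. The loose reading has support inside item 8 itself: B and C join up in whole millimetres only if the lower sign means up to and including, and the upper sign means from that value on. One, three, and five or more stents score 0, 1 and 2 in both rows. Two stents (0 or 1) and four stents (1 or 2) are open, which makes 2 × 2 = 4 complete sets.

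**Item D.** Grades coded: none, mild, moderate, severe. Grades scored: mild = 1, severe = 2. None is naturally 0. Moderate lies between two adjacent scores and could be 1 or 2.

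**Items B, C, E, F.** Whole-millimetre values without a score are 35 and 71 in B, and 20 and 31 in C; fractional values between 35 and 36, 70 and 71, 20 and 21, and 30 and 31 are also missed. E is complete. F prints no score for a straight vessel, naturally 0.

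**Effect on one patient.** For four stents and moderate calcification, A + D runs from 1 + 1 = 2 to 2 + 2 = 4.

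**Illustration of choosing late.** Assume that a single item is tested as a linear trend against restenosis, that there is no true association, and that the better of two codings is reported. The two test statistics then correlate as the two codings do, r = Cov(s1, s2) / √(Var s1 × Var s2), and the false-positive rate is P(|Z1| > 1.96 or |Z2| > 1.96) for a bivariate normal with correlation r. All shares below are assumed.

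- *D*, none/mild/moderate/severe scored (0,1,1,2) or (0,1,2,2), with the other three grades sharing the rest equally. Moderate at 25%: r = 0.50 / √(0.50 × 0.6875) = 0.853, rate 7.4%. At 10%: r = 0.933, 6.7%. At 40%: r = 0.791, 7.9%.
- *A*, last two table rows. One to five stents equally common: r = 0.40 / √(0.40 × 0.80) = 0.707, rate 8.3%. Shares of 35/35/18/8/4%: r = 0.558, 8.9%. Shares of 20/40/25/10/5%: r = 0.517, 9.0%.
- If all six items were summed (A, B and C uniform on 0 to 2, E on 1 to 3, F on 0 to 3, all independent), the item D choice alone would give about 5.7% to 6.1%.

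**The case against.** **These are typing slips, or signs lost when the PDF was read.** Partly right. A lost bar under an inequality sign cannot be excluded, although such signs survive elsewhere, as in "J-CTO score of ≥ 2 was defined as complex". But a lost bar does not settle item A: different restorations give different scores to two and four stents. It has no bearing on item D, where two lists of words disagree.

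**Item D need not use the grades of Methods 2.** Item 8 does not say that it does; the link is inferred. It is a fair inference, because item F repeats the tortuosity definitions from the same paragraph, and no other calcification grading is given.

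**The plan contains no trend test.** This stands. Methods 4 names chi-square or Fisher tests, forward stepwise logistic regression and Cox regression. If calcification entered a model by its four coded grades, the score for moderate would not matter.

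**B, C and F are copy-edits.** This stands too; they belong in the same correction but carry little weight.

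A reader might infer that scoring two to four stents as 1 is the only possible repair of item A, and hence that moderate calcification is the only real choice left. The documents do not support this. It follows only if the outer bands of A are taken strictly, while B and C use the same signs loosely.

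**Conclusion.** The point holds, as a minor one. Item 8 is a rule that fails when followed, not merely one short of detail. Three scores are open (two stents, four stents, moderate calcification); the remaining gaps have obvious repairs.

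The reach is limited to a secondary endpoint of an exploratory study. The primary endpoint, binary restenosis at 13 months, does not use the score. How many patients are affected is unknown, because the documents give no distribution of stent counts or calcification grades.

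A reader might take the 7% to 9% range as the error rate that the trial will have. The documents do not support that: the trend test, the shares and the choice of the better coding are all assumptions, and the plan does not say how the R-score is to be analysed.

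**What to change.** Before any 13-month angiogram is read, and without outcome data, replace the bands in Methods 3, item 8 so that every recorded value has exactly one score:

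- **A:** the sponsor confirms either 1 stent = 0, 2 to 4 = 1, more than 4 = 2 (printed outer bands kept) or another complete set, so that two and four stents each have a fixed score.
- **D:** none = 0, mild = 1, severe = 2, with moderate fixed by the sponsor at 1 or 2.
- **B and C:** close the gaps, for example up to 35, >35 to 70 and >70 mm; and up to 20, >20 to 30 and >30 mm.
- **E:** no change.
- **F:** straight = 0.

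Add one sentence saying whether the six items are summed or analysed separately.

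The cost is a few words of text, with no extra data or patients. The downside is that the sponsor commits now to scores that it may have preferred to leave open, and the printed limits of B and C move by up to 1 mm.
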